1.1.3 Clinical

The previously completed B01-02 Phase 2 study examined a single, 1.2 billion cell dose of MultiStem administered 24 to 48 hours following an acute ischemic stroke. The B01-02 study design was double-blinded, randomized, and placebo-controlled with 134 subjects enrolled/dosed and was conducted at 33 sites in the United States and the United Kingdom. ¹⁴ Eligible subjects had to have suffered a cortical cerebral ischemic stroke with moderate to moderately-severe disability (National Institutes of Health Stroke Scale [NIHSS] scores 8 to 20), as measured at Baseline at least 24 hours from the time of stroke onset.

The B01-02 study data showed MultiStem cell therapy to be well tolerated and associated with a favorable impact on a range of complications and outcomes following ischemic stroke. ¹⁵ In all subjects treated with 1.2 billion MultiStem cells 24 to 48 hours after stroke onset, the MultiStem group showed a trend for benefit compared to the placebo group in Excellent Outcome at Day 90 (modified Rankin Scale [mRS] ≤1; NIHSS ≤1; and Barthel Index ≥95), and this effect was significant by Day 365. The study also showed that earlier administration (≤36 hours) was associated with significant difference between MultiStem and placebo in the distribution of mRS scores, and higher rates of subjects achieving an Excellent Outcome at Day 90 and/or Day 365. Additionally, early MultiStem treatment (≤36 hours) was associated with accelerated recovery for some subjects, as is evident in the proportion of MultiStem subjects relative to placebo subjects achieving a mRS score of ≤2 or Barthel Index score of ≥95 at Day 30.

Treatment with 1.2 billion MultiStem cells was shown to be safe and generally well tolerated throughout the B01-02 study. Additionally, the results showed MultiStem to be associated with a favorable impact on a range of complications and outcomes following ischemic stroke including a reduced incidence of deaths, life-threatening adverse events, urinary tract infection, and secondary infection rates compared to placebo. Additionally, the mean duration of hospitalization and the

mean duration of stay in an intensive care unit (ICU) were shorter in the MultiStem compared to the placebo group.

Through Year 1, MultiStem-treated subjects in the B01-02 study generally continued to improve compared to placebo subjects, as evident in multiple measures of neurological function. For example, at 90 days, early-treated MultiStem subjects (≤36 hours) had a higher proportion of Excellent Outcomes (i.e., full or nearly full recovery) than placebo subjects (16.1% v. 6.6%). By 1 year, 3.5 times as many of the early-treated MultiStem subjects achieved the Excellent Outcome endpoint compared to placebo subjects (29.0% v. 8.2%, p<0.01). Finally, the available data suggest that MultiStem could provide functional and clinical benefit to subjects with moderate and moderately-severe strokes, subjects who have received reperfusion therapy as well as those who have not, and younger and older stroke subjects.

1.2 Rationale

More than 300 subjects have been administered single or multiple doses of MultiStem cell therapy (ranging from approximately 20 million to 1.2 billion total cells) in Phase 1 and 2 clinical studies for acute myocardial infarction, hematopoietic malignancy transplant, liver transplant, ulcerative colitis, acute respiratory distress syndrome, and ischemic stroke. To date, adverse events have been consistent with the disease states being studied in ongoing and completed studies, and MultiStem treatment has been well tolerated (see the Investigator's Brochure for further information).

MultiStem cell therapy for the treatment of ischemic stroke has the potential to target multiple reparative, anti-inflammatory, and cytoprotective processes after stroke onset. MultiStem can be delivered intravenously and has a wider target therapeutic time window than tPA. MultiStem has the potential to provide a new treatment option for patients suffering from this common, life-threatening and disabling condition for which very limited treatment options currently exist. Current therapies have limited efficacy, impart a significant risk of potentially devastating complications, and are administered to only a small minority of ischemic stroke patients due to the limited treatment time window, as well as contraindications and/or restrictions for use.

Overall, the aforementioned clinical and non-clinical data demonstrate that human MultiStem cells have been adequately characterized and supports safe progression into the current Phase 3 study, which will examine the effect of MultiStem cell therapy compared to placebo on functional outcomes and safety in subjects dosed 18 to 36 hours after suffering a moderate to moderately-severe acute, ischemic stroke.

2 STUDY OBJECTIVES

2.1 Primary Objective

The primary objective of this study is to evaluate the efficacy of MultiStem on functional outcome in subjects with ischemic stroke.

2.2 Secondary Objectives

The secondary objectives of this study are the following:

- To evaluate the efficacy of MultiStem on functional, neurological, mortality, secondary infection, and hospitalization outcomes in subjects with ischemic stroke; and
- To evaluate the safety of MultiStem in subjects with ischemic stroke.

2.3 Tertiary Objectives

The tertiary objectives of this study are the following:

- To evaluate the impact of MultiStem on quality of life and healthcare and rehabilitation services utilization in subjects with ischemic stroke; and
- To evaluate the mechanism of action of MultiStem through blood biomarkers, and spleen and brain imaging outcomes in subjects with ischemic stroke.

3 STUDY DESCRIPTION

3.1 Summary of Study Design

This is a pivotal Phase 3, randomized, double-blind, placebo-controlled, multicenter international study. The total study duration for safety follow-up will be 12 months. Approximately 300 subjects who have experienced an acute cortical ischemic stroke and fulfill all the eligibility criteria will be enrolled into the study in approximately 50 to 60 sites globally.

Approximately 300 subjects will be randomized in a 1:1 ratio (MultiStem [n=150]) or placebo [n=150]) to receive a single IV infusion of 1.2 billion cells of MultiStem. Randomization will be stratified by Baseline NIHSS score (\leq 12 and \geq 13), concomitant reperfusion therapy (Yes or No), and age (18 to 64 and \geq 65 years). All subjects will be enrolled continuously into the study. Enrollment of subjects receiving concomitant reperfusion therapy (tPA, mechanical reperfusion [MR], or tPA + MR) will be limited to 40% of the entire randomized study population (approximately 120 subjects) with the tPA + MR sub-group being limited to 10% of the entire randomized study population.

Protocol stopping rules will be in place, with an independent Data Safety Monitoring Board (DSMB) assembled if serious safety events, including infusion reactions, occur related to investigational product. In addition, the DSMB will meet during the subject enrollment period to examine the unblinded safety data.

Subjects will be evaluated at Baseline, prior to infusion and post-infusion, 24 hours from the start of the infusion, 48 hours from the start of the infusion, Day 7, Day 30, Day 90, Day 180, and Day 365, or at the Early Termination (ET) Visit. To prevent subjects from being lost to follow-up, study sites will contact subjects every other month (Day 60, Day 150, Day 210, Day 270, and Day 330 [±7 days]) remotely to update the subject's medical status and disposition.

At the Screening Visit, subjects or legally authorized representatives (LARs) will provide written informed consent and undergo standard of care procedures, evaluation for inclusion/exclusion criteria, medical history, a physical examination, height and weight, pulse oximetry, concomitant medication assessments, 12-lead electrocardiogram (ECG), blood safety laboratory assessments, pregnancy testing, vital sign assessments, NIHSS assessment, pre-stroke mRS historical assessment, and brain magnetic resonance imaging (MRI)/computed tomography (CT).

The Screening Barthel Index score can be collected any time prior to the start of the infusion.

At the Baseline Visit (Day 0), subjects will be re-evaluated for inclusion/exclusion criteria, undergo a physical examination, vital signs, pulse oximetry, adverse event (collection begins from the start of the infusion) and concomitant medication assessments, blood safety laboratory collection, allogeneic antibody and exploratory blood biomarker collections, and a NIHSS assessment.

Subjects meeting eligibility requirements will be randomized and receive an IV infusion of MultiStem or placebo (18 to 36 hours post-stroke).

During the study, assessments of safety will include the evaluation of adverse events and concomitant medications, clinical laboratory results, allogeneic antibody testing, vital signs, pulse oximetry, 12-lead ECGs, and physical examinations. Efficacy will be assessed by mRS, NIHSS, Barthel Index, and EuroQol 5 dimensions (EQ-5D) scores. Healthcare and rehabilitation services

utilization will be assessed during the study. Exploratory blood biomarkers will be assessed at Baseline and during the study.

Subjects at selected sites will undergo ultrasound of the spleen and brain MRI (diffusion tensor imaging [DTI]) at Baseline (prior to the start of the infusion) and throughout the study to explore the mechanism of action of MultiStem.

3.2 Study Indication

MultiStem is an allogeneic, RMAT indicated for treatment of acute ischemic stroke within 36 hours after symptom onset.

4 SELECTION AND WITHDRAWAL OF SUBJECTS

4.1 Inclusion Criteria

Subjects will be eligible for the study if they meet all of the following inclusion criteria:

- 1. Male or female subjects 18 years of age or older;
- 2. Clinical diagnosis of ischemic stroke involving cerebral cortex;
 - o This inclusion criterion requires clinical signs that are consistent with imaging abnormalities required under inclusion criterion #5. Clinical diagnosis is defined as rapidly developed clinical signs of 1 or more focal (and potentially accompanying global) persistent disturbance(s) of cerebral function, with no apparent cause other than arterial occlusive ischemic stroke that involves cerebral cortex;
- 3. Onset of stroke symptoms must have occurred 18 to 36 hours prior to the planned start of administration of the investigational product;
 - Note: Time of onset is defined as the time point, if known, when symptoms first began. For a stroke that occurred during sleep, or in an individual unable to report the time that symptoms began, the time of onset is defined as the time point when the subject was last observed to exhibit normal neurological function or was self-reported to have normal function;
- 4. Occurrence of a moderate to moderately severe stroke with a persistent neurologic deficit documented by a NIHSS score of 8 to 20 (inclusive) that does not change by ≥4 points from the Screening to the Baseline assessment;
 - Note: The Screening NIHSS score used for determination of eligibility should be collected as soon as possible following admission to the hospital. In the event a subject receives concomitant reperfusion therapy the subject's Screening NIHSS score is encouraged to be collected prior to any concomitant reperfusion therapy but can be collected as late as 4 hours following completion of the last reperfusion (mechanical or pharmacologic) therapy;
- 5. Confirmation of hemispheric cortical infarct by brain MRI or CT demonstrating an acute ischemic infarct measuring ≥5 mL and ≤100 mL;
- 6. A mRS score of 0 or 1 prior to the onset of symptoms of the current stroke, by either self-reported history or by family/caregiver report;
- 7. Female subjects must not be pregnant, breastfeeding, or planning on becoming pregnant during the study; and either:
 - a. Not of childbearing potential, defined as one who has been postmenopausal for at least 1 year, or has been surgically sterilized; or
 - b. Agree to use a medically accepted, effective method of avoiding pregnancy through the Day 90 Visit. Effective methods of contraception are defined as those that result in a low failure rate (<1% per year) when used consistently and correctly. Such methods include the use of oral contraceptives, other hormonal contraceptives (vaginal products, skin patches, or implanted or injectable products), or mechanical products (such as an intrauterine diaphragm, condoms, or spermicides);

- 8. Male subjects with female sexual partners of childbearing potential must also agree to use an effective method of avoiding pregnancy through the Day 90 Visit;
- 9. Subjects or legally authorized representatives must freely sign the informed consent form (ICF) after the nature of the study and the disclosure of his/her data have been explained;
- 10. Willing and able to comply with all aspects of the treatment and testing schedule; and
- 11. Willing and able to return to the study site for the post-treatment evaluations.

4.2 Exclusion Criteria

Subjects will not be eligible for the study if they meet any of the following exclusion criteria:

- 1. Presence of a lacunar or a brainstem infarct on MRI or CT as the etiology of current stroke symptoms;
- 2. Coma (score of 3 for item 1a of NIHSS);
- 3. Occurrence of a hemorrhagic transformation of ischemic stroke as evidenced by brain MRI or CT that is clinically significant in the opinion of the Investigator;
- 4. Fluctuation in neurologic status since the onset of stroke suggesting possible progression or expansion of stroke, transient ischemic attack, or stroke mimic;
- 5. Onset of stroke >28 hours prior to the start of Screening;
 - Note: Onset of stroke >28 hours prior to the start of Screening would not allow for administration of investigational product per protocol;
- 6. Less than 6 hours between the Screening and Baseline NIHSS assessment;
- 7. Initiation of IV tPA infusion >4.5 hours and/or MR (defined as time of groin puncture) >8 hours after the onset of stroke;
 - Note: tPA implies not only recombinant human tissue plasminogen activator, but also its engineered derivatives, including tenecteplase, Retavase[®], and potentially other such agents that might conceivably reach the market (once they are approved and including desmoteplase, lanoteplase, etc.);
- 8. Plan to have a neurovascular procedure (e.g., carotid endarterectomy, stent placement, etc.) within the first year following stroke;
- 9. Pre-existing ipsilateral focal neurologic deficits that would complicate evaluation;
- 10. Seizure since the onset of stroke or prior history of seizures, with the exception of simple febrile seizures in childhood;
- 11. Major neurologic event such as stroke or clinically significant head trauma in the 6 months preceding study entry;
- 12. Uncontrolled hypertension prior to randomization, defined as persistent systolic blood pressure >220 mmHg or diastolic blood pressure >120 mmHg despite antihypertensive therapy;
- 13. Blood glucose level <50 mg/dL or >350 mg/dL prior to randomization despite concomitant therapy;

- 14. Significant comorbid medical condition(s), including, but not limited to:
 - a. End-stage renal disease requiring renal replacement therapy;
 - b. Advanced liver disease (e.g., Childs-Pugh score >10);
 - c. Severe congestive heart failure (e.g., New York Heart Association score of III or IV) or ejection fraction <30%;
 - d. Severe lung disease requiring continuous home oxygen; or
 - e. Symptomatic refractory angina requiring daily treatment with nitrates or other medications;
- 15. Concurrent systemic infection or severe local infection;
- 16. Immunocompromised state due to immunosuppressive medications or as evidenced by hematologic studies or history of opportunistic infection;
- 17. History of Alzheimer's disease or other dementias, Parkinson's disease, or any other neurological disorder that in the opinion of the Investigator would affect the subject's ability to participate in the study or confound study assessments;
- 18. History of malignancy of any type within 2 years of stroke onset, with the exception of adequately treated basal or squamous cell carcinoma of the skin;
- 19. Life expectancy less than 90 days;
- 20. Prior surgical removal of the spleen or functional asplenia;
- 21. Allergy or religious objections to human tissue or bovine or porcine products;
- 22. Participation in any other study involving an investigational product or device within the last 30 days or planned participation in investigational rehabilitation stroke recovery program; or
- 23. Other serious medical or psychiatric illness that is not adequately controlled and, in the Investigator's opinion, would not permit the subject to be managed or evaluated according to the protocol.

4.3 Withdrawal Criteria

Participation of a subject in this clinical study may be discontinued for any of the following reasons:

- The subject or LAR withdraws consent or requests discontinuation from the study for any reason; or
- Termination of the study by the Sponsor or the regulatory authority.

If a subject withdraws prematurely from the study due to the above criteria or any other reason, study staff should make every effort to complete the full panel of assessments scheduled for the ET Visit (Day 365/ET). The reason for subject withdrawal must be documented in the electronic case report form (eCRF).

Every effort should be made to minimize the number of subjects for whom follow-up data are not collected as missing data can adversely affect the validity or interpretation of the study results.

Withdrawn subjects will not be replaced.

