4.3.1 Lost to Follow-up

In the case of subjects lost to follow-up, attempts to contact the subject must be made and documented in the subject's medical records. A file will be considered closed after the site completes 3 phone calls followed by a certified letter to the last known address of the subject with no response obtained.

Every effort should be made to minimize the number of subjects for whom follow-up data are not collected as missing data can adversely affect the validity or interpretation of the study results.

Every effort will be made by the Investigator to contact the subject before the subject is declared lost to follow-up. This level of diligence is necessary to obtain (at a minimum) vital status (whether the subject is alive) and thus avoid lost to follow-up for efficacy and safety assessment. All sites will receive training on how vital status may be collected and monitored in accordance with local/legal practices and ethical regulations for all subjects randomized, including those who did not receive investigational product.

If vital status is determined, the subject will not be considered lost to follow-up.

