Note: The post-infusion visits may be conducted remotely if the subject is unable to attend the site visit. It is preferable to perform a remote visit rather than have the subject miss the visit; the possibility of a remote visit and the procedures to be conducted need to be discussed with the Sponsor in advance.

6.4.1 24 Hours From the Start of the Infusion (± 6 Hours)

The following procedures will be performed at 24 hours from the start of the infusion:

- Perform a physical examination;
- Perform a 12-lead ECG;
- Obtain vital signs;
- Perform pulse oximetry;
- For subjects in the sub-study only: perform a spleen ultrasound;
- Obtain blood sample for chemistry and hematology testing (central laboratory); and
- Assess adverse events and record concomitant medications.

6.4.2 48 Hours From the Start of the Infusion (±6 Hours)

The following procedures will be performed at 48 hours from the start of the infusion:

- Perform a 12-lead ECG;
- Obtain vital signs;
- Perform pulse oximetry;
- For subjects in the sub-study only: perform a spleen ultrasound;
- Obtain blood sample for chemistry and hematology testing (central laboratory);

- Obtain blood sample for exploratory blood biomarkers; and
- Assess adverse events and record concomitant medications.

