6.4.6 Day 90 (±7 Days)

The following procedures will be performed at Day 90:

- Determine NIHSS score;
 - Note: NIHSS assessments are preferred to be completed in a face-to-face setting. If conducted remotely, telemedicine is acceptable, and telephone is not acceptable. NIHSS assessments for post-Baseline visits must be completed by staff who are certified in NIHSS administration. Effort should be made to have the same assessor complete all post-Baseline visit assessments for an individual subject when possible. The possibility of a remote visit and the procedures to be conducted need to be discussed with the Sponsor in advance;
- Determine mRS score;
 - Note: mRS assessments are strongly preferred to be completed in a face-to-face setting. If face-to-face assessment is not possible, assessments may be conducted remotely by telemedicine. Only as a last resort in extraordinary circumstances, if telemedicine is not possible, telephone assessment is permitted. Effort should be made to have the same assessor complete all post-Baseline visit assessments for an individual subject when possible. When evaluating subjects to determine the mRS score, the raters of the score must not make any attempt to exclude or correct for disability that the rater attributes to causes other than stroke. The score should be recorded without regard to the cause of the disabilities that impact the score or the time point at which the disabilities occurred. The possibility of a remote visit and the procedures to be conducted need to be discussed with the Sponsor in advance;
- Determine Barthel Index score;
 - Note: Barthel Index assessments are strongly preferred to be completed in a face-to-face setting. If face-to-face assessment is not possible, assessments may be conducted remotely by telemedicine. Only as a last resort in extraordinary circumstances, if telemedicine is not possible, telephone assessment is permitted. Effort should be made to have the same assessor complete all post-Baseline visit assessments for an individual subject when possible. The possibility of a remote visit and the procedures to be conducted need to be discussed with the Sponsor in advance;
- Record the date the subject was admitted to and/or discharged from the ICU, the hospital, and to a non-hospital residential care facility following the initial stroke;

- For subjects in the sub-study only: perform a brain MRI-DTI;
- Measure health-related quality of life with the EQ-5D questionnaire;

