6.5 Day 365 (±7 Days)/Early Termination Visit and Withdrawal Procedures

The end of treatment for subjects completing the study is Day 365. For subjects who are withdrawn from the study prior to completion, all Day 365 procedures will be performed at the ET Visit.

Note: The post-infusion visits may be conducted remotely if the subject is unable to attend the site visit. It is preferable to perform a remote visit rather than have the subject miss the visit; the possibility of a remote visit and the procedures to be conducted need to be discussed with the Sponsor in advance.

The procedures to be conducted at Day 365/ET include the following:

- Perform a physical examination;
- Obtain vital signs;
- Perform pulse oximetry;
- Determine NIHSS score;
 - Note: NIHSS assessments are preferred to be completed in a face-to-face setting. If conducted remotely, telemedicine is acceptable, and telephone is not acceptable. NIHSS assessments for post-Baseline visits must be completed by staff who are certified in NIHSS administration. Effort should be made to have the same assessor complete all post-Baseline visit assessments for an individual subject when possible. The possibility of a remote visit and the procedures to be conducted need to be discussed with the Sponsor in advance;

• Determine mRS score:

Note: mRS assessments are strongly preferred to be completed in a face-to-face setting. If face-to-face assessment is not possible, assessments may be conducted remotely by telemedicine. Only as a last resort in extraordinary circumstances, if telemedicine is not possible, telephone assessment is permitted. Effort should be made to have the same assessor complete all post-Baseline visit assessments for an individual subject when possible. When evaluating subjects to determine the mRS score, the raters of the score must not make any attempt to exclude or correct for disability that the rater attributes to causes other than stroke. The score should be recorded without regard to the cause of the disabilities that impact the score or the time point at which the disabilities occurred. The possibility of a remote visit and the procedures to be conducted need to be discussed with the Sponsor in advance;

- Determine Barthel Index score;

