9 STATISTICS

9.1 Analysis Populations

9.1.1 Intent-to-Treat Population

The Intent-to-Treat Population will include all randomized subjects. This population will be used for the primary and key secondary efficacy analyses.

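### A subject who leaves the study but still permits contact has no planned Day 90 or Day 365 mRS, so an early exit score stands in for it

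*Protocol*

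**What the plan says.** Section 4.3 of the protocol lists two grounds for ending participation. One is termination of the study. The other is "The subject or LAR withdraws consent or requests discontinuation from the study for any reason". For any premature withdrawal, "study staff should make every effort to complete the full panel of assessments scheduled for the ET Visit", and the reason is entered on the eCRF. Section 6.5 repeats this: "For subjects who are withdrawn from the study prior to completion, all Day 365 procedures will be performed at the ET Visit". That panel includes the mRS, NIHSS and Barthel Index. No section schedules contact after it.

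The protocol also contains provisions that bear on retention:

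- Section 4.3: "Every effort should be made to minimize the number of subjects for whom follow-up data are not collected". No procedure is attached.
- The notes opening 6.4, repeated in 6.5, allow remote post-infusion visits for a subject who is unable to attend: "It is preferable to perform a remote visit rather than have the subject miss the visit".
- Section 6.4.6 allows the Day 90 mRS by telemedicine and, as a last resort, "if telemedicine is not possible, telephone assessment is permitted". Section 7.2.2 says the same for the mRS in general.
- Section 4.3.1, on subjects lost to follow-up: "This level of diligence is necessary to obtain (at a minimum) vital status (whether the subject is alive". Sites are trained to collect vital status for everyone randomized.

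On analysis, 9.1.1 states: "The Intent-to-Treat Population will include all randomized subjects. This population will be used for the primary and key secondary efficacy analyses". Section 9.2.1.1 fills a missing Day 90 mRS with the last post-Baseline score before Day 90, and 9.2.1.2 applies LOCF to the key secondary endpoints, the first of which is excellent outcome at Day 365.

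**The concern.** Treatment is one infusion on Day 0. Once it has been given, a request to discontinue can only concern follow-up. Withdrawing consent to all contact and ending participation while still accepting an occasional call are different situations, because in the second the endpoint can still be measured. The protocol has no status for the second. The only concrete instruction at exit is a panel dated by the exit, not by the endpoint window.

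The primary question is function at Day 90 in all randomized subjects. If someone leaves on Day 20 and the text is followed literally, the Day 20 mRS becomes the Day 90 value while recovery may still be under way. An exit before Day 365 does the same to the first key secondary endpoint. The substituted score may be too bad (recovery continues) or too good (later deterioration). If exits differ between arms in number or in kind, the treatment comparison shifts, and the direction cannot be known in advance.

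**Working it through.** **1. The passages side by side.** The remote-visit notes apply to a subject who stays in the study and cannot attend. Section 4.3 applies to a subject who leaves. Neither refers to the other. The vital-status effort in 4.3.1 reaches all randomized subjects, but knowing that a subject is alive gives no mRS grade. So the means of obtaining a late mRS exist and are not connected to the exit procedure.

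**2. The plan's own power figures.** Inputs: Table 1 rates rescaled to 100% (the rows sum to 99.9% and 100.1%), mRS 5 and 6 pooled, unstratified Wilcoxon test, 1-sided alpha 0.025, 200,000 simulated trials per cell. At 150, 141 and 135 per group this gives 95.4%, 94.1% and 93.3%. Table 2 states 95%, 94% and 93%, so the figures reproduce. Table 2 assumes complete cases and completely random dropout, so it does not describe a carried-forward exit score.

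**3. How many subjects.** In B01-02 the non-completers were 3 + 14 + 5 + 1 = 23. Without the 14 deaths that is 9/129 = 7.0%. The protocol expects 6% to 7% here: 0.06 × 300 = 18 and 0.07 × 300 = 21. Two things reduce the number this point concerns:
- The rate covers a full year, so only part falls before the Day 90 window.
- The nine were 3 consent withdrawals before dosing, 5 lost to follow-up and 1 withdrawn by the Investigator. None is listed as a dosed subject asking to stop.

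**4. Effect on the treatment measure.** The plan's measure is P(MultiStem better) − P(placebo better), computed here without strata as D = Σ t(i)·P(C > i) − Σ c(i)·P(T > i), where t and c are the Table 1 proportions and T and C the mRS grades in the two arms.
- Wins: 0.0400×1 + 0.1552×0.9321 + 0.2893×0.6613 + 0.2663×0.3646 + 0.1752×0.2208 = 0.512
- Losses: 0.0679×0.8048 + 0.2707×0.5155 + 0.2967×0.2492 + 0.1439×0.0741 = 0.279
- D = 0.233, or 23.3 points

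Now let a fraction f of an arm carry a score k grades worse than its true Day 90 score, capped at the pooled 5/6 category. The arm's distribution becomes (1 − f)·p + f·p shifted by k. Both f and k are assumptions; the protocol gives neither.

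| f, MultiStem / placebo | k = 1 | k = 2 |
|---|---|---|
| 6% / 2% | 21.6 | 20.1 |
| 2% / 6% | 24.6 | 25.3 |
| 7% / 7% | 22.9 | 22.3 |

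The imbalanced cases move D by 1.3 to 3.2 points. The sampling standard error of D at 150 per arm, simulated from Table 1, is about 6.3 points.

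**5. Effect on power,** same simulation, with 6% and 7% of Day 90 scores missing:

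| Handling | 6% | 7% |
|---|---|---|
| Complete cases | 94.2% | 94.0% |
| Carried scores follow each arm's own distribution, one grade worse | 94.8% | 94.7% |
| Carried MultiStem scores follow the placebo distribution | 92.8% | 92.1% |
| Carried scores in both arms follow the pooled distribution, one grade worse | 92.6% | 92.0% |

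With every Day 90 score obtained, power is 95.4%.

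**The case against.** The strongest reply is that the protocol already covers most of this. It asks for every effort against missing follow-up, prefers a remote visit to a missed one, repeats that note in the section on withdrawal procedures, allows telephone mRS, schedules remote contacts to prevent loss to follow-up, and plans sensitivity analyses for missing data. A sensible site might well call a departed but willing subject at Day 90, and nothing forbids it.

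Much of that stands, and it rules out several stronger readings:

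- A reader might infer that someone who merely wants fewer site visits is pushed out of the study. The criterion concerns discontinuing from the study, participation may rather than must end, and the remote-visit note offers such a subject a route.
- A reader might infer that the Day 90 mRS is lost. The ET panel includes an mRS, and LOCF carries a pre-Day 90 score forward. The value is substituted, and even that is the likely result of the text rather than something it prescribes.
- A reader might infer that nearly all of the 18 to 21 expected discontinuations could be rescued. The B01-02 reasons do not support this.
- A reader might take it as established that these exits depend on outcome. That is plausible, but no figure in the protocol shows it.

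What the reply does not remove is that the remote-visit note is worded for inability to attend, 4.3 does not refer to it, and no instruction links a subject who has left to the endpoint windows.

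**Conclusion.** The gap is real and modest. Withdrawal of consent and a request to discontinue share one consequence, and no provision asks for the mRS in the Day 90 or Day 365 window from a subject who leaves but still permits contact. Under intent-to-treat with LOCF, an early score then enters the primary analysis and the Day 365 key secondary analysis.

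The size is probably small. With arm imbalances of four percentage points and exit scores one or two grades worse, the win difference shifts by at most 3.2 points, about half its standard error. Equal 7% rates shift it by 0.4 points (one grade) or 1.0 (two grades). Power stays between 92.0% and 94.8% with 6% to 7% missing. These results rest on Table 1 being true, on an unstratified calculation, and on assumed imbalances and grade shifts. They also treat all expected non-death discontinuation as occurring before Day 90, which overstates the Day 90 effect. The protocol's power figures are not in error. The case for the change is that it adds real endpoint data at little cost.

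**What to change.** In 4.3, separate two situations and record on the eCRF which applies:

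- **(a) The subject stops participation but allows contact.** Do the ET panel, then obtain the mRS and Barthel Index remotely in the Day 90 and Day 365 windows. State in 6.5 that an ET Visit does not replace these assessments.
- **(b) The subject withdraws consent to all contact.** Do the ET panel if the subject agrees, then apply the vital-status provision of 4.3.1 where local law allows.

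The consent form needs matching wording.

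The cost is protocol and consent text plus one or two remote contacts for a small number of subjects. The downside is that some scores will be rated by telephone rather than face to face, which the protocol already accepts for the mRS and Barthel Index as a last resort. It does not accept telephone for the NIHSS, so a telephone-only contact leaves the NIHSS part of the excellent-outcome endpoint open unless the mRS or Barthel Index already fails its threshold. Telemedicine is therefore preferable where the subject agrees.
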